NCT03628872

Title: Er:YAG versus Scaling and Root Planing for the Treatment of Periodontal

Disease: A Single-Blinded Split-Mouth Randomized Clinical Trial

Protocol Version #: Laser2017v1

IRB Approved Effective Date: 01/26/2018

Protocol: AAAR6077

Protocol Status: Approved Effective Date: 01/26/2018

Expiration Date: 01/09/2019

Principal Investigator: [name]

Co-investigator and lead author: [name]

Co-investigator: [name] Co-investigator: [name]

Title: Er:YAG versus Scaling and Root Planing for the Treatment of Periodontal Disease: A

Single-Blinded Split-Mouth Randomized Clinical Trial

Protocol Version #: Laser2017v1

Abbreviated Title: Treatment of Periodontitis with Er:YAG laser

BACKGROUND

STUDY PURPOSE AND RATIONALE

The purpose of this study was to examine the changes in clinical parameters 3 months after non-surgical periodontal treatment was performed with two different treatment modalities, conventional scaling and root planing and Er:YAG laser.

STUDY DESIGN

The study was conducted as a randomized, split-mouth clinical trial. Thirty subjects were recruited and right and left side (upper and lower quadrant on each side) of the patients' mouths were randomly assigned to the two treatment modalities:

1. Conventional scaling and root planing:

Treatment was performed with Cavitron® and hand instrumentation (11/12 and 13/14 gracey's, 11/12 and 13/14 mini gracey's, 4R/4L curette and sickle scaler)

2. Er:YAG laser:

Treatment was performed with Cavitron® and the laser set at 50 mJ and 20pps, with water irrigation (set at 10) and air cooling (set at 7). C400F and PS600T tips (J. MORITA MFG. CORP, Kyoto, Japan) were used. Er:YAG was used for further calculus removal; root debridement and decontamination; ablation of the epithelial lining to avoid downgrowth of epithelium; and ablation of diseased connective tissue, in the inner surface of the gingival epithelium and/or in any existing vertical defect. Removal of inflamed epithelial and connective tissues on the external surface was also achieved in order to promote faster inflammation reduction. Subsequently, blood coagulation was accomplished with defocused irradiation and without the cooling water spray. Irradiation was accomplished using the tip parallel to the root surfaces, starting at the deepest portion of the periodontal pocket, in a sweeping motion, slowly moving towards the coronal aspect of the pocket.

Inclusion criteria:

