- Signed and dated Informed Consent
- Good general health
- Participants ≥ 18 years of age
- Participants with ≥ 20 teeth with 5 teeth, including at least 1 molar, in each quadrant of the mouth
- Participants with $\geq 30\%$ of the present teeth with Probing depths of > 4mm and BoP
- Non-smoker and former smokers (stopped smoking > 1 year)
- Participants that have not received any periodontal treatment in the past 3 months

Exclusion criteria:

- Participants with uncontrolled systemic diseases that could affect the treatment outcome such
 as Diabetes with HbA1c > 7.0 percent, rheumatoid arthritis, immunosuppression, HIV with
 detectable viral loads
- Participants requiring antibiotic prophylaxis for any cardiovascular conditions or after any transplant and/or replacement procedures
- Pregnancy
- Patients treated with systemic antibiotic therapy of periodontal/mechanical/local delivery therapy within 6 weeks prior to study entry and throughout the study duration
- Patients being chronically (two weeks or more) treated with any NSAIDs, steroids or any medications known to affect soft tissue condition (excluding treatment with Acetylsalicylic acid < 100 mg/day)
- Presence of orthodontic appliances, or any removable appliances that impinges on the tissues being assessed
- Presence of soft or hard tissue tumors of the oral cavity
- The presence of any medical or psychiatric condition or any other condition that, in the opinion of the Investigator, could affect the successful participation of the patient in the study

RECRUITMENT

All patients seen in the pre-doctoral and post-doctoral clinics at Columbia University College of Dental Medicine were considered as potential subjects, and all students, residents and faculty were informed of this study. If any patient met the inclusion/exclusion criteria and showed interest, the study provider was contacted to provide the patient with more information.

STUDY PROCEDURES

Microsoft ® Excel software was used to generate the random sequence that allocated right and left sides (including upper and lower quadrant on each side) to the treatment modalities. Randomization was kept in an encrypted computer to which only the provider had access to. Allocation was revealed only to provider immediately prior to the first treatment appointment.

Examiner was blinded with respect to which one of the two therapies was rendered during the entire duration of the study.

VISITS:

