- 1ST VISIT: Review electronic health records, including medical history, medications and dental x rays, check inclusion and exclusion criteria, solve any questions the patient may have and obtain informed consent. The following clinical parameters were recorded: clinical attachment level (CAL), pocket depths (PD), bleeding on probing (BoP) and plaque index (PI), all of them recorded in 6 sites per tooth, and tooth mobility. Patient was given oral hygiene instructions.
 - 2ND VISIT*: Review electronic health records, including medical history, medications. Oral inspection. Treatment of the assigned side, both upper and lower quadrants, after randomization, with conventional scaling and root planing. Patient will be given oral hygiene instructions. Anesthesia: Inferior alveolar blocks for the mandible and local infiltration for the maxilla with Lidocaine 2% 1:100,000 epinephrine for healthy patients Carbocaine 3% no epinephrine for patients with cardiovascular issues.
- 3RD VISIT*: Review electronic health records, including medical history, medications. Oral inspection. Treatment of the assigned side, both upper and lower quadrants, after randomization, with Er:YAG laser therapy. Patient will be given oral hygiene instructions. Anesthesia: Inferior alveolar blocks for the mandible and local infiltration for the maxilla with Lidocaine 2% 1:100,000 epinephrine for healthy patients Carbocaine 3% no epinephrine for patients with cardiovascular issues.
- 4TH VISIT, 1 month follow up. Review electronic health records, including medical history, medications. Patient was given oral hygiene instructions.
- 5TH VISIT, 3 months follow up. Review electronic health records, including medical history, medications. The following clinical parameters were recorded: CAL, PD, BoP and PI, all of them recorded in 6 sites per tooth, and tooth mobility. Periodontal maintenance with Cavitron ® and hand instruments (11/12 and 13/14 gracey's, 11/12 and 13/14 mini gracey's, 4R/4L curette and sickle scaler) was performed. Patient was given oral hygiene instructions.
- * 2^{ND} and 3^{RD} appointments were given within 10 days of each other in order to complete non-surgical periodontal treatment of the whole mouth within that period of time.

INFORMED CONSENT PROCESS

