Informed consent with written documentation was obtained from the research participant, by study provider. Due to the high number of Hispanic patients that were expected to be recruited, informed consent in English and Spanish was created and approved by Columbia University's Rascal.

OBJECTIVES

The primary objective of the present study was to compare periodontal clinical parameters (CAL, PD, BoP and PI) after non-surgical periodontal therapy completed with the afore mentioned treatment modalities.

Secondary objectives included record the differences in duration of treatment between the 2 arms of the study, assessing the differences in sensitivity, and evaluate subjects' modality of preference.

POTENTIAL RISKS AND BENEFITS

Therapy for periodontal disease could involve slight soreness and sensitivity, manageable with any *over-the-counter* analgesic. Soft gingival tissues could experience shrinkage due to resolution of inflammation, situation in which clinical crowns of the treated teeth could appear to be slightly longer than previous to the therapy performed.

There is no direct benefit for participating in the study; participants will be contributing to research for treating periodontal disease. However, after treatment, gingival inflammation, sensitivity, soreness, spontaneous or induced bleeding and halitosis will improve after periodontal therapy. Once the etiology of periodontal disease, bacteria, is removed, we hope to arrest the disease progression with the provided active therapy and the subsequent recall visits.

The alternative is not to participate in the study. However periodontal disease should, in all cases, be treated. The alternatives patients would have, are either to refuse all proposed treatments or to undergo therapy with only conventional hand instruments.

STATISTICAL PROCEDURES

Wilcoxon signed-rank test will be performed to assess the significance of the results pertaining to CAL and PPD (significance level of 5%). Student's t test to analyze BOP scores (significance level of 5%) SAS 9.2

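### The signed-rank test for CAL and PPD names no test variable, baseline adjustment, effect estimate or interval; adjusting for the baseline already recorded costs no data and usually improves precision

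*Combined protocol and SAP*

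**What the plan says.** STATISTICAL PROCEDURES gives CAL and PPD one sentence: "Wilcoxon signed-rank test will be performed to assess the significance of the results pertaining to CAL and PPD (significance level of 5"%). BOP gets a Student's "t test to analyze BOP scores (significance level of 5"%). Nothing says what is ranked, at what unit, or whether baseline enters, and no estimate or interval is mentioned. I take PPD to be the PD recorded at the visits.

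Two places point to different test variables. STUDY PURPOSE AND RATIONALE sets out to "examine the changes in clinical parameters 3 months after non-surgical periodontal treatment", which suggests change scores. OBJECTIVES makes the primary aim "to compare periodontal clinical parameters (CAL, PD, BoP and PI) after non-surgical periodontal therapy", which suggests 3-month values.

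The data for adjustment exist. STUDY DESIGN: "Thirty subjects were recruited and right and left side (upper and lower quadrant on each side"). STUDY PROCEDURES describes a "random sequence that allocated right and left sides (including upper and lower quadrant on each side) to the treatment modalities". Under VISITS, the first visit records "clinical attachment level (CAL), pocket depths (PD), bleeding on probing (BoP) and plaque index (PI), all of them recorded in 6 sites per tooth", and the 3-month visit records "CAL, PD, BoP and PI, all of them recorded in 6 sites per tooth, and tooth mobility".

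**The concern.** Each patient supplies a laser-minus-SRP difference before treatment and another at 3 months. Testing 3-month values leaves the first unused. Testing changes uses it, but with the slope fixed at 1. Which is more powerful depends on r and on the ratio of the two SDs, and neither is in the documents. Estimating the slope avoids having to guess. The open wording also allows the variable to be chosen after the data are seen.

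Separately, a p-value alone cannot say how far the modalities differ, and that is what the primary objective asks.

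The point concerns only the comparison between modalities. Within-side tests of baseline against 3 months, which the wording does not exclude, are not affected.

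**Working it through.** **Inputs from the documents:** 30 patients, one side per treatment, 5% level, CAL and PD on both sides at both visits. Two-sided testing is assumed because sidedness is not stated. The documents give no power, effect, SD or correlation, so there is no figure of the plan's own to reproduce.

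**Assumptions:** one mean per side per patient; a true 3-month difference of 0.45 SD; r varied; SDs equal at the two visits unless stated; no ties and no dropout.

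**Definitions:** D0 and D1 are the laser-minus-SRP differences at baseline and 3 months. The adjusted variable is D1 − b·D0, with b = Σ(D0·D1)/Σ(D0²), the slope through the origin.

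**Variance** (D1 variance = 1, n = 30): values 1; changes 2(1 − r); adjusted about (1 − r²)(n − 2)/(n − 3) = (1 − r²) × 28/27.

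| r | values | changes | adjusted | 30 adjusted pairs equal, on values / changes |
|---|---|---|---|---|
| 0 | 1 | 2.0 | 1.037 | 28.9 / 57.9 |
| 0.3 | 1 | 1.4 | 0.944 | 31.8 / 44.5 |
| 0.5 | 1 | 1.0 | 0.778 | 38.6 / 38.6 |
| 0.7 | 1 | 0.6 | 0.529 | 56.7 / 34.0 |
| 0.9 | 1 | 0.2 | 0.197 | 152.3 / 30.5 |

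Simulated interval widths agree. At r = 0.5 the mean 95% widths are 0.673 adjusted and 0.757 on values, and 30 × (0.757/0.673)² = 38.

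**Power** (%, simulation; exact signed-rank critical value 137, size 0.0497; values / changes / adjusted; a dash means not tabulated):

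| Data | r = 0 | r = 0.3 | r = 0.5 | r = 0.7 |
|---|---|---|---|---|
| Normal | 64.8 / 38.3 / 63.1 | 64.5 / 50.4 / 66.7 | 64.6 / 64.3 / 74.9 | 64.3 / 85.3 / 88.9 |
| Laplace | 77.5 / 44.5 / 75.1 | 75.2 / 58.0 / 78.2 | 72.7 / 72.8 / 84.6 | 71.3 / 91.1 / 94.2 |
| t, 3 df, independent errors | 87.1 / 54.8 / 84.8 | 85.3 / 70.3 / 87.7 | 82.9 / 82.9 / 92.0 | 82.5 / 96.1 / 97.7 |
| t, 3 df, elliptical | 87.6 / – / 85.0 | 87.4 / 75.9 / 87.4 | 87.5 / 87.8 / 92.4 | 87.8 / 97.3 / 97.6 |
| Normal, 3-month SD 0.7 × baseline | – | – | 65.0 / 45.1 / 75.4 | 64.6 / 62.4 / 88.9 |
| Normal, 3-month SD 1.3 × baseline | – | – | 64.0 / 72.9 / 74.7 | 64.2 / 90.4 / 89.2 |

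- Gain over the better reading at r = 0.3: 0.0 (elliptical) to 3.0 (Laplace).
- At r = 0.5: 1.8 (SD ratio 1.3) to 11.8 (Laplace).
- At r = 0.7: −1.2 (SD ratio 1.3) to 3.6 (normal), apart from SD ratio 0.7, where it is 88.9 − 64.6 = 24.3.
- Gain over the worse reading for r from 0.3 to 0.7: 92.4 − 87.5 = 4.9 to 75.4 − 45.1 = 30.3.
- No gain at the ends of the range: at r = 0.2, 64.1% on values against 64.0% adjusted (normal); at r = 0.9, 100.0% on changes against 99.9%.
- Largest average loss: 87.6 − 85.0 = 2.6 points.

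The SD ratio matters because the ideal slope is r × ratio. At r = 0.7 and ratio 1.3 it is 0.91, so a fixed slope of 1 is nearly right. At ratio 0.7 it is 0.49, so it is not.

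**Chance baseline imbalance.** When the mean of D0 is not zero, the through-origin slope absorbs part of the effect: the mean of D1 − b·D0 shrinks by the factor 1 − mean(D0)²/mean(D0²). Among normal trials with |z| of mean D0 above 1.5 (about 15% of trials), power on values against adjusted is 66% against 55% at r = 0, a loss of 11 points. At r = 0.3 it is 64% against 57%, a loss of 7 points; a longer run of the same case gave 63% against 58%, so read this as 5 to 7. At r = 0.3 the values test is itself conditionally biased in such trials: at |z| = 1.5 the shift is 0.3 × 1.5/√30 = 0.08 SD.

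**Level.** Swapping a patient's side labels reverses the signs of D0 and D1 together, so D0·D1, D0² and hence b do not change. With no difference between modalities and independent side allocation, the exact signed-rank distribution therefore still applies. Simulated type I error is 0.0493 to 0.0504. A slope fitted with an intercept lacks this property and gives 0.0573 to 0.0597.

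**The case against.** The strongest reply is that the benefit rests on numbers the documents do not contain. On the changes reading, which the purpose statement supports, baseline is already used, and at high r little or nothing is left to gain. Gains over the worse reading partly measure ambiguity, which one clarifying sentence would cure. Naming the variable and adding a Hodges–Lehmann estimate with its interval would repair the plain omissions without a less familiar test. The imbalance cost is real, and recruitment and measurement are already written in the past tense.

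Much of this stands, and it is why the sizes are given as conditional ranges. But naming the variable alone still commits the trial to a guess about r and the SD ratio, and baseline costs nothing more to use.

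Three stronger readings might be inferred, and the documents support none of them.

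- *The planned test is biased or has the wrong level.* Sides are randomised, so with one mean per side per patient either unadjusted reading is valid. Testing sites as if independent would put the level at stake, but the plan names no unit, and that is a separate matter.
- *Baseline is ignored.* That holds only on the values reading.
- *Adjustment reliably adds about ten points.* That needs r near 0.5 and favourable SDs and data shape. Elliptical tails give 4.6 points there, and an SD ratio of 1.3 gives 1.8.

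**Conclusion.** The concern holds as a conditional loss of precision, together with three plain omissions: the test variable, the baseline adjustment, and an estimate with its interval. For moderate r the adjusted signed-rank test is usually better than either unadjusted reading and seldom much worse on average. It is not uniformly better: it gains nothing at the ends of the range of r, can lose about 1 point to changes when the 3-month SD is larger, and costs more in trials with baseline imbalance and low r. These sizes rest on the assumed effect, correlations, SD ratios and data shapes. The need for an estimate and interval does not depend on r. This change should be made, but it is not a fault that invalidates the trial.

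**What to change.** 1. Use one mean per side per patient and form D0 and D1.
2. Primary test for CAL and PPD: the planned signed-rank test applied to D1 − b·D0, with b = Σ(D0·D1)/Σ(D0²). Do not use an intercept-fitted slope in this test.
3. Report the effect with a 95% interval by inverting this test. For each trial shift δ, replace D1 by D1 − δ, refit b, and keep the shifts that are not rejected. Refitting keeps the level argument valid at every shift and makes the interval agree with the p-value.
4. Sensitivity analysis: the unadjusted signed-rank test, stating whether it uses 3-month values or changes, with its Hodges–Lehmann estimate and interval.
5. Any regression intercept is supportive only and need not agree with the primary p-value. A least-squares test should not decide. It does slightly better with normal data (77% against 75% at r = 0.5), but with independent 3-df tails at r = 0 it has 74% power against 87% for the unadjusted test on values.
6. Date the change before analysis, which may still be possible because the test is written in the future tense. Otherwise label it post hoc.

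Cost: analysis-plan wording and modest SAS programming, mainly for the interval; no new data. Downsides: a small average loss of power if r is near 0, more under baseline imbalance, and a linear baseline relation assumed for the gain (not for the level).

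### The BOP analysis names a Student's t test without saying that it is paired, does not define the BOP score, and makes no use of the baseline BoP that is recorded

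*Combined protocol and SAP*

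**What the plan says.** Under Study Design, "Thirty subjects were recruited and right and left side" were randomised between the two treatments. Study Procedures confirms that the random sequence "allocated right and left sides (including upper and lower quadrant on each side) to the treatment modalities". Every patient therefore supplies one laser side and one conventional side.

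Objectives states that the primary aim is to "compare periodontal clinical parameters (CAL, PD, BoP and PI) after non-surgical periodontal therapy", so BOP is a primary-objective parameter.

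Under Visits, the 1st visit records "bleeding on probing (BoP) and plaque index (PI), all of them recorded in 6 sites per tooth", and the 3-month visit again records "CAL, PD, BoP and PI, all of them recorded in 6 sites per tooth". Baseline and 3-month BoP are thus both available on both sides.

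Statistical Procedures has two analysis statements. For attachment level and pocket depth, "Wilcoxon signed-rank test will be performed to assess the significance of the results pertaining to CAL and PPD". For BOP, "Student's t test to analyze BOP scores (significance level of 5" per cent). The word paired appears nowhere. No section turns the site readings into a BOP score, and the analysis makes no mention of baseline BoP. Study Purpose and Rationale speaks of changes in the clinical parameters at 3 months, but the statistical section does not carry this through.

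**The concern.** In a split-mouth trial the treatment comparison lies within the patient. The signed-rank test implies that pairing. The name Student's t test does not, because it covers a paired and a two-sample form. An analyst could run the two-sample form on side scores and still be within the wording. If the two sides of a mouth bleed alike, that analysis uses a standard error that is too large, and a real BOP difference can be missed in a trial of only 30 patients.

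Two related gaps sit beside this. The unit of analysis is not stated, and baseline BoP, which may explain part of the 3-month difference between sides, is left unused.

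**Working it through.** The plan gives no power, SD, correlation or effect size, so it has no figure of its own to reproduce. The calculations below are illustrations.

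**Inputs from the documents.** 30 patients, two sides each (Study Design); 5% level (Statistical Procedures); 6 sites per tooth (Visits); "5 teeth, including at least 1 molar, in each quadrant of the mouth" (Inclusion criteria).

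**Assumptions.** Two-sided tests, bivariate normal side scores with equal SD, and left-right correlation ρ of 0, 0.3, 0.5 or 0.7.

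**Step 1: standard errors.** With SD σ per side score and n = 30:

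- true variance of the mean difference = 2σ²(1 − ρ)/n
- variance that the two-sample test uses = 2σ²/n
- ratio of standard errors = 1/√(1 − ρ) = 1.00, 1.20, 1.41 and 1.83 at ρ = 0, 0.3, 0.5 and 0.7.

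The estimated difference is the same under both tests.

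**Step 2: type I error and power** (simulated, 30 pairs; first three result columns 1,000,000 draws per cell):

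| ρ | Type I error, two-sample | Power at 0.5 SD, two-sample | Power at 0.5 SD, paired | Power at 0.4 SD, two-sample | Power at 0.4 SD, paired |
|---|---|---|---|---|---|
| 0 | 5.0% | 48% | 46% | 33% | 32% |
| 0.3 | 2.1% | 47% | 61% | 30% | 43% |
| 0.5 | 0.7% | 47% | 75% | 27% | 56% |
| 0.7 | 0.08% | 47% | 93% | 23% | 78% |

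The paired test holds 5% at every ρ. Two-sample power is flat at 0.5 SD only because 0.5/√(2/30) = 1.94 lies close to the critical value of the test. At 0.4 SD it falls as ρ rises.

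**Step 3: unit of analysis.** Each side has at least 2 quadrants × 5 teeth × 6 sites = 60 sites. Testing single sites as independent would ignore clustering. With 40% bleeding, a patient variance of 0.10 and a side variance between 0 and 0.10 on a latent scale, all assumed, simulated type I error ran from about 4% to about 38%. The documents do not say where in such a range the trial would fall, so no size is claimed.

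**Step 4: using baseline.** Let D₀ and D₃ be the laser-minus-conventional differences at baseline and 3 months. Fit D₃ = a + bD₀ without centring D₀. The intercept a is the expected difference when the two sides start equal. Fitting the change instead gives D₃ − D₀ = a + (b − 1)D₀, with the same a and the same standard error.

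If r is the correlation of D₀ with D₃, the width of the confidence interval relative to the paired t test is about √(1 − r²) × 1.019, where 1.019 is the simulated ratio at r = 0:

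- r = 0.3: 0.954 × 1.019 = 0.97
- r = 0.5: 0.866 × 1.019 = 0.88
- r = 0.7: 0.714 × 1.019 = 0.73

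Simulation (200,000 draws) gave 1.019, 0.973, 0.883 and 0.728 at r = 0, 0.3, 0.5 and 0.7. Type I error was 5.0% to 5.1%. Power was 79%, 82%, 89% and 97% where the paired t test has about 80%.

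**The case against.** The best defence is that the wording is silent on pairing and does not specify a two-sample test. The title and Study Design say split-mouth, every patient supplies both sides, and the neighbouring sentence names a paired test. Pairing is the natural inference. This stands: a reader might infer that the plan prescribes the wrong test, and the documents do not support that.

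A reader might also infer that the BOP analysis risks false positives, because BoP is read at many sites. That would require single sites to be the unit, which the plan does not say and which is the less natural reading. The missing unit is also not peculiar to BOP, since attachment level, pocket depth and plaque are recorded in the same way with no summary defined.

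It is fair to add that the loss under the two-sample form rests wholly on an assumed ρ, and that adding the word paired with a definition of the score would remove the ambiguity. Baseline adjustment goes further; its case is likely precision at small cost, and a paired t test without it would still be valid.

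Finally, recruitment and visits are described largely in the past tense, so the wording may only be settled before analysis and not before data collection. None of this supplies the missing specification.

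**Conclusion.** The point holds as an ambiguity and a cheap improvement; it does not show an invalid analysis. A paired t test on one score per patient-side has no validity problem. A two-sample test on the same scores would leave the estimate unchanged and, for non-negative ρ, would not raise false positives. Its cost is precision: at ρ of 0.3 to 0.7 its real type I error is about 2% down to below 0.1%, and for a 0.5 SD difference it gives up about 14 to 46 percentage points of power (61 − 47 and 93 − 47). At ρ = 0 nothing is lost. These sizes depend on assumed correlations and approximately normal side scores. The documents fix neither, and they give no basis for sizing the site-level problem.

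**What to change.** Before analysis, replace the BOP sentence with:

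> BOP will be summarised as one score per treated side per patient (for example the percentage of bleeding sites, if BoP is recorded yes/no). The within-patient difference (laser minus conventional) at 3 months will be analysed by linear regression on the within-patient difference in baseline BOP, not mean-centred. The intercept, with its two-sided 5% test and 95% CI, is the treatment effect. An unadjusted paired t test on the same within-patient differences will be reported as a sensitivity analysis.

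Because the adjusted effect is the same for 3-month values and for changes, this also serves the aim in Study Purpose and Rationale.

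The cost is a few sentences, one degree of freedom and slightly more analysis work. No new data are needed. The confidence interval is about 2% wider than that of the paired t test if baseline predicts nothing, and 3%, 12% or 27% narrower at an assumed correlation of 0.3, 0.5 or 0.7 between baseline and 3-month differences.

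The minimum acceptable change is to state a paired t test on one score per patient-side. The same line should then say whether 3-month values or changes are tested, since without adjustment the two can differ.
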